- Secondary objective: To evaluate novel Sleep Revolution diagnostic variables and their relation to symptom burden, patient 's help request during baseline assessment and outcome of sleep apnea treatment with CPAP after 3 months.
- Further secondary objectives: Feasibility and safety of the self-applied sleep testing and the digital platform for both sleep and symptom assessment

Study Design:

The study is performed at 24 sites of the European Sleep Apnea Database (ESADA) network in 15 European countries. Most relevant details of the study design are listed below:

- Study SR-001 is a multi-center, 2-arm, cross-over study comparing the diagnostic impact and accuracy of two different diagnostic pathways on the outcome of diagnosis and CPAP treatment in patients with suspected OSA. Patients referred to one of 24 sleep centers of the ESADA network participating in the Sleep Revolution project will be studied using both the clinical routine of OSA evaluation (standard care) and the novel Sleep Revolution based diagnostic pathway including self-applied polysomnography over three nights, digitally based symptom evaluation, and actigraphy based assessment of sleep wake rhythm and physical activity (experimental condition). Study participants will be randomized with respect to the order of two diagnostic pathways. The decision on diagnosis and treatment will be based on information from the first diagnostic procedure (SC or SR), the results from the second pathway will be blinded both to the investigator (sleep specialist) and the patient.
- Following diagnostic steps including sleep testing, symptom assessment and evaluation of physical status evaluation, patients will receive information regarding the sleep disorder diagnosis by the sleep specialist. In case of a diagnosis of clinically relevant OSA, treatment recommendations will be provided. Only patients initiating therapy with PAP will be approached for participation in the subsequent part of the study- treatment start and follow up for 3 months.

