 - Epworth Sleepiness Scale, Insomnia Severity Index, Fatigue Severity Scale, Pittsburgh Sleep Quality Inventory, Depression Anxiety Stress Scale – short version with 21 questions (DASS21), Clinical Global Impression Scales

Capacity of the novel SR diagnostic pathway to detect clinically significant sleep apnea

Sleep apnea severity and sleep quality

SR procedure: 3 nights: Means, Minimum, and Maximum for: AHI, ODI, T90, Total Sleep Time, % sleep stage distribution, hypoxic burden assessed by ABOSA software

- Standard care procedure: AHI, ODI, T90, Total Sleep Time, % sleep stages, hypoxic burden assessed by ABOSA software
- "First night" and "between night" effects: Differences between nights 1, 2 and 3 in the sleep recording results, in particular night 1 versus 2 or 3. Analysis of variability: %supine position, REM-sleep%, and alcohol intake prior to sleep (dichotomic)
- Frequency of OSA diagnosis in Standard Care versus SR care
- Frequency of no sleep apnea, and "mild to severe" OSA according to the AHI criteria AHI<5, 5-<15, 15-<30 and ≥ 30 events/hour in both arms (SR and SC)
- Frequency of treatment recommendations
- Distribution of recommendation for PAP, OD, surgery, weight reduction, no treatment for the two randomised patient groups: Standard care versus Sleep Revolution based diagnosis
- Frequency of other sleep diagnoses in Standard Care versus SR care
- Frequency of insomnia, combined OSA and insomnia (COMISA), Periodic Limb Movement Disorders (PLMD), Restless Legs Syndrome (RLS)

Prespecified subgroup analyses:

- Sex, even pre-post menopause
- Technical feasibility analysis: Age stratification by tertiles
- Weight change group in the PAP follow-up study

Clinically meaningful outcomes of CPAP treatment in patients with OSA

• Adherence with and efficacy of PAP treatment

Mean values for the treatment period, variability of PAP use over time, residual AHI, leakage.

CPAP-non users: Identification of those patient characteristic: more complex analysis of predictors for PAP non -users by parameters from the diagnostic process (standard care and SR case)

• Effects of PAP treatment

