- Change in physiological data like AHI, blood pressure, weight, sleep test data (sleep stages, oxygenation), as well as APP derived cognitive function, and more subjective data like the ESS scores, questionnaires, and the ESQ follow up module; Sleep App parameters: overall wellbeing, treatment rating by the patient, sleep habits (diary), degree of physical activity (subjective ratings). All those data need to be adjusted for PAP adherence.
- Comparison between objective changes by treatment (see point above) with patient reported perception of treatment (data from the questionnaires and APP) through descriptive analysis, correlation analysis and cluster analysis
- Comparison of objective and subjective patient changes with the rating of the sleep doctors in the CGI-change by treatment scale.

Feasibility of the European Sleep Questionnaire (both technical failure and patients ´ inability to perform the SAP)

- Time spent to fill in the questionnaire, even possible or subparts of the questionnaire
- Completeness of data in the ESQ
- Subgroup analysis separated by age and sex
- Patients feedback

Feasibility of the SR digital platform for data transfer

- Percentage missing data, data transfer failure rate, patient experience, health care personnel experience
- Safety and tolerability of self-applied polysomnography
- Patient centred reporting of clinical symptoms in a digital platform

The predictive value of the sleep related novel variables detected by the SR diagnostic pathway (hypoxic burden (ABOSA software), symptom burden (ESQ based data) for three months treatment outcome after CPAP therapy:

- o symptom improvement following therapy: daytime sleepiness and sleep quality
- adherence with PAP treatment (hours used, number of patients with PAP adherence at least 3 or 4 hours, proportion of PAP non acceptance)
- o comparison of outcomes with parameters from standard care

Exploratory Objectives

- Proportion of patients diagnosed with clinically relevant sleep apnea in each arm, proportion of patients with treatment recommendations for CPAP, mandibular advancement devices, or upper airway surgery in each arm of the study.
- Proportion of patients with PAP non-adherence (user time <4h/night) in each study arm
- Sleep apnea alleviation by PAP (calculation of overall efficacy of PAP adjusted for PAP adherence, mean habitual sleep time and residual AHI during PAP use)

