All reported AEs will be listed and compared in the two study groups. The incidence of PAP treatment-emergent AEs will be included in incidence tables. Events with missing onset dates will be included as treatment emergent. If a patient experiences more than 1 occurrence of the same AE, the occurrence with the greatest severity and the closest association with the study treatment will be used in the summary tables. SAEs and AEs causing discontinuation will be tabulated. All AEs will be listed by patient, along with information regarding onset, duration, relationship and severity to study treatment, action taken with study treatment, treatment of event, and outcome.

- Vital signs like blood pressure and heart rate will be summarized using descriptive statistics, including mean values and mean change from baseline values, as well as numbers of patients with values outside limits of the normal range at each time point.
- Summary tables will be provided for concomitant medications initiated during the study period.

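### The rule for missing onset dates counts every undated adverse event as PAP treatment-emergent, without requiring that the patient started PAP or that the event could have followed PAP start

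*SAP*

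**What the plan says.** The safety analysis in SAP section 8.5 (Example 3) contains four relevant statements.

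- All events are kept in a group comparison: "All reported AEs will be listed and compared in the two study groups".
- One category is tabulated by incidence, and it is tied to PAP: "The incidence of PAP treatment-emergent AEs will be included in incidence tables".
- The next sentence deals with missing dates: "Events with missing onset dates will be included as treatment emergent".
- A full listing is also planned: "All AEs will be listed by patient, along with information regarding onset, duration, relationship and severity to study treatment".

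On who receives PAP, section 3 (Study Design) says: "Only patients initiating therapy with PAP will be approached for participation in the subsequent part of the study". Section 4 expects other outcomes of the diagnostic process for some patients and plans to tabulate them: "Distribution of recommendation for PAP, OD, surgery, weight reduction, no treatment for the two randomised patient groups".

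Safety of the diagnostic technology is itself of interest. Section 3 (Study Objective) lists "Feasibility and safety of the self-applied sleep testing and the digital platform for both sleep and symptom assessment", and section 4 lists "Safety and tolerability of self-applied polysomnography".

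**The concern.** Counting an undated event as treatment-emergent is a familiar cautious convention. It works well when nearly everyone receives the study treatment soon after enrolment, because an undated event then most likely did follow treatment start. This trial has two stages. Every randomised patient is to undergo diagnostic testing, by both pathways, and PAP comes later and only for some. An undated event may therefore belong to the diagnostic phase, and in a patient who never starts PAP it cannot be emergent on PAP at all.

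What is at stake is the correctness of the PAP incidence tables. A programmer who implements the sentence as written would put an undated skin reaction during home testing, in a patient who was never given PAP, into a table headed PAP treatment-emergent. The numerator would then include people outside the exposed population, and readers would attribute to PAP events that did not arise on it. No primary or efficacy inference is affected.

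**Working it through.** The SAP states no AE figure that could be reproduced, so the check is mainly a reading of the passages together.

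**Step 1: what the category means.** Section 8.5, Example 3, uses the term treatment-emergent in two consecutive sentences. The first ties it to PAP and the second gives the missing-date rule. No other treatment-emergent category appears in that section. Section 4 (Safety Endpoints) names treatment-emergent events but ties them to no other treatment.

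**Step 2: who can be in the category.** Sections 3 and 4 together give three kinds of undated event:

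| Undated event | Can it be PAP-emergent? | Class under the rule as written |
|---|---|---|
| In a patient who never started PAP | No | PAP treatment-emergent |
| In a PAP starter, arising before PAP start | No | PAP treatment-emergent |
| In a PAP starter, arising after PAP start | Yes | PAP treatment-emergent |

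The rule is right for the third row only. In the second row it is defensible where nothing else dates the event, but the sentence makes no exception for events that other recorded information places earlier.

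**Step 3: how a set of undated events would divide (assumptions only).** Let m be the number of undated events, s the share of patients starting PAP, and q the share of starters' undated events that arose in the diagnostic phase. Assume the events are spread evenly over patients. Take m = 20, s from 0.4 to 0.8 and q from 0.25 to 0.75.

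- Never on PAP: m(1 − s) = 20 × 0.2 to 20 × 0.6 = 4 to 12.
- Starters, before PAP: m·s·q = 20 × 0.4 × 0.25 to 20 × 0.8 × 0.75 = 2 to 12.
- Truly PAP-emergent: m·s(1 − q) = 20 × 0.4 × 0.25 to 20 × 0.8 × 0.75 = 2 to 12.
- Misclassified in total: 20 − 12 = 8 to 20 − 2 = 18.
- In the all-AE comparison and the listing: 20 in every scenario.

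**Step 4: effect on an incidence among starters (assumptions only).** Take 1,000 randomised (the SAP's 500 per group). Assume 550 PAP starters, 55 of them with a true PAP-emergent AE (55/550 = 10.0%), 100 patients with a diagnostic-phase AE, and 5-15% of those onsets missing, which is 5 to 15 events. If events are spread evenly, 55% fall in starters: 0.55 × 5 = 2.75 to 0.55 × 15 = 8.25. If each adds a new patient to the table, the incidence becomes (55 + 2.75)/550 = 10.5% to (55 + 8.25)/550 = 11.5%. On the same assumptions a further 0.45 × 5 = 2.25 to 0.45 × 15 = 6.75 events come from patients with no PAP exposure and have no valid place in the table.

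**The case against.** The strongest reply is that the rule follows directly on a sentence about PAP events, and that an event cannot emerge on PAP in someone never exposed. The natural reading would then be that it resolves undated events within PAP starters, where it is a common and cautious choice. The SAP does not expressly say that non-starters enter the table, and a treatment-emergent window or partial-date rule may stand in the protocol, which is not at hand.

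Part of this stands. Within starters the convention is reasonable where nothing else dates the event, and the sponsor may well intend a table of starters only. But the sentence as written carries no such limit, and even a starters-only table would take in events known from other information to precede PAP.

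A reader might go further and infer that undated events are removed from the safety data on self-applied testing, so that diagnostic-phase incidence is understated while PAP incidence is overstated. The SAP does not support that. Every AE, dated or not, remains in the two-group comparison and in the by-patient listing, and nothing says that a treatment-emergent flag removes an event from another summary. The SAP defines no diagnostic-phase AE table, window or denominator, so there is no stated incidence to be understated. Patient-reported tolerability of the self-applied procedure (section 8.6) is untouched by the rule.

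**Conclusion.** Wrong as written, in a narrow sense. The rule is stated without condition, attaches to PAP, and does not fit a design in which only a subset starts PAP after a separate diagnostic phase. It can misattribute undated diagnostic-phase events to PAP, including events in patients never exposed.

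The conclusion rests on the wording of section 8.5 and on the two-stage design in section 3, and needs no assumed rate. The size does need assumptions. AE rates, missing-date share and PAP uptake are all absent from the SAP, and the figures in the working show only the direction and the mechanism. The real effect is probably small and is confined to descriptive safety tables.

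**What to change.** Replace the missing-date sentence in section 8.5, Example 3, with a conditional rule along these lines:

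> An AE with a missing or incomplete onset date is classed as PAP treatment-emergent only if the patient started PAP and no other recorded information (partial date, stop date or recording visit, where captured) places its onset before PAP start. In patients who did not start PAP, undated AEs are classed as diagnostic-phase events. The denominator of the PAP treatment-emergent table is the number of patients who started PAP. The number of events classified by this rule is reported.

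The cost is a short text change and a little more programming. It should be made before the AE tables are produced. Slightly fewer events will be counted as PAP treatment-emergent. If stop date or recording visit is not held in the database, the rule falls back on PAP start alone, which still removes the never-exposed patients.

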8.6. Exploratory Analysis

Drop out analysis: Factors predicting loss of data in the SR care pathway (sleep test, SR App, ESQ)

Results from bio-sample analysis (baseline, treatment response)

- \circ $\;$ Feasibility and rate of completeness using three nights SAS procedure $\;$
- Patient reported tolerability of the SAS procedure

8.7. Subgroup Analysis

The following subgroup analyses will be performed for secondary and exploratory analyses:

- Males and Females in each group
- Age group 18-<45 y, 45-<65 y, 65 years and more
- Subgroups of patients studied in the standard care pathway using different settings:
 - Polysomnogrpahy (AASM level 1 and 2) versus cardiorespiratory polygraphy (level 3)
 - Home sleep testing versus in sleep laboratory assessment
 - o Manual sleep test scoring versus automated scoring

8.8. Sensitivity Analysis

Sensitivity analyses for secondary, tertiary, and exploratory endpoints will be performed according to the outlines above in case of imputation of larger amounts of data (>10%), log transformation of data, or in subgroup analyses specified above.

8.9. Interim Analysis

In the original protocol, an interim analysis was planned after the first 500 patients from the 24 study centers. However, the Sleep revolution Executive Committee decided not to perform an interim analysis due to the following reasons:

- No safety objective with the new technology
- Not feasible to stop the trial over several months (already delayed due to COVID 19)
- Good recruitment over the entire spectrum of centers
- To maintain highest statistical power for the primary and secondary outcome analyses
- Risk for unbalanced recruitment in individual ESADA centers due to time delay

8.10. Imputation of missing data

In the event of missing data, standard imputation procedures will be employed to ensure the robustness of the statistical analysis. The following steps will be taken to handle missing data: 1. Identification of Missing Data: The dataset will be examined to identify any missing values in the variables of interest.

2. Assessment of Missing Data Mechanism: The mechanism of missing data (Missing Completely at Random, Missing at Random, or Missing Not at Random) will be assessed to determine the appropriate imputation method.

3. Imputation Methods:

- Mean/Median Imputation: For continuous variables, missing values may be imputed using the mean or median of the available data.

- Regression Imputation: Missing values may be imputed using regression models that predict the missing values based on other available variables.

- Multiple Imputation: Multiple imputation techniques may be employed to create several imputed datasets, which will be analyzed separately and combined to produce overall estimates. In case of Multiple imputation, the method of chained equations (MICE package in R) may be performed if needed.

4. Sensitivity Analysis: Sensitivity analyses will be conducted to assess the impact of the imputation on the results. Different imputation methods will be compared to ensure the robustness of the findings.

5. Documentation: All imputation procedures and decisions will be thoroughly documented to ensure transparency and reproducibility of the analysis.

9. Handling of Missing Data

- Method of Handling Missing Data: See chapter 8.10 above.
- Sensitivity to Missing Data: See chapter 8.10 above.

10. Data Monitoring and Quality Assurance

- Data Monitoring:
 - The study will be monitored according to the monitoring plan to ensure that it is conducted and documented properly according to the protocol, GCP, and all

applicable regulatory requirements. The monitoring function will be organized by the study centres at Reykjavik University and Gothenburg University.

- Monitoring visits, on-site or remote (telephone/video meetings) and contacts will be made at appropriate times during the study. The Principal Investigator at each study site will assure he/she and adequate site personnel are available throughout the study to collaborate with clinical monitors. If necessary, clinical monitors must have direct access to source documentation in order to check the completeness, clarity, and consistency of the data recorded in the eCRFs for patients included in the study.
- The investigator at site will make available to the clinical monitor all source documents and medical records necessary to review protocol adherence and eCRFs. In addition, the investigator will work closely with the clinical monitor and, as needed, provide them appropriate evidence that the study is being conducted in accordance with the protocol, applicable regulations, and GCP guidelines.

• Quality Assurance Procedures:

- The central study coordinator or its designee will perform the quality assurance and quality control activities of this study; however, responsibility for the accuracy, completeness, security, and reliability of the study data presented to RU lies with the local investigator generating the data.
- RU, the EU grant provider or the central study coordinator, may arrange audits as part of the implementation of quality assurance to ensure that the study is being conducted in compliance with the protocol, standard operating procedures, GCP, and all applicable regulatory requirements. Audits will be independent of and separate from the routine monitoring and quality control functions. Quality assurance procedures will be performed at study sites and during data management to assure that safety and efficacy data are adequate and well documented.

11. Assumptions and Statistical Considerations

• Normality Assumptions:

To ensure the validity of the statistical tests, the following assumptions will be tested: 1. Normality: The normality of residuals will be assessed using the Shapiro-Wilk test, Q-Q plots, and histograms of residuals. If the residuals deviate significantly from normality, transformations (e.g., log transformation) or non-parametric methods may be considered.

2. Independence: The independence of observations will be checked by examining the study design and ensuring that there is no clustering or repeated measures within the same group. For mixed-effects models, the random effects will account for potential clustering.

3. Homoscedasticity: Homoscedasticity (constant variance of residuals) will be assessed using residual plots (residuals vs. fitted values). If heteroscedasticity is detected, robust standard errors or weighted least squares may be used.

4. Linearity: The linearity of relationships between predictors and the outcome will be checked using scatter plots and residual plots. Non-linear relationships may be

addressed using polynomial terms or splines in the model.

5. Multicollinearity: Multicollinearity among predictors will be assessed using Variance Inflation Factors (VIF). Predictors with high VIF values may be removed or combined to reduce multicollinearity

• Transformation of Data:

To meet the assumptions of statistical tests, data transformations may be applied as necessary. For example, if the data is highly skewed, a log transformation or other appropriate transformation will be considered to normalize the distribution. The choice of transformation will be based on the nature of the data and the specific assumptions of the statistical tests being used.

• Outlier Handling:

Outliers can significantly impact the results of statistical analyses. The following steps will be taken to identify and manage outliers in the dataset:

1. Identification of Outliers:

Visual Inspection: Box plots and scatter plots will be used to visually inspect the data for potential outliers. Statistical Methods: Z-scores and the IQR (Interquartile Range) method will be used to identify outliers. Data points with Z-scores greater than 3 or less than -3 will be considered outliers. Additionally, data points falling below Q1 - 1.5*IQR or above Q3 + 1.5*IQR will be flagged as outliers.

2. Management of Outliers:

Verification: Outliers will be verified to ensure they are not data entry errors. If an outlier is determined to be an error, it will be corrected or removed. Sensitivity Analysis: Analyses will be conducted with and without outliers to assess their impact on the results. Transformation: If outliers are not errors and cannot be removed, data transformation techniques (e.g., log transformation) may be applied to reduce their impact. Robust Methods: Robust statistical methods that are less sensitive to outliers (e.g., median-based measures) may be used.

The decision to retain or exclude outliers will be documented, and the rationale for the decision will be provided.

12. Software and Tools

Statistical Software:

The statistical programs SPSS and the R software package R version 4.3.1, located in a data cluster at Reykjavik University, Iceland, are available. All analysis will be performed by authorized personnel on this cluster.

• Data Management Software: REDCap and Excel are used for data management.

13. Reporting and Interpretation of Results

• Presentation of Results:

Results will be clearly presented using tables, figures, and confidence intervals: **Tables** will summarize descriptive statistics, model estimates, and p-values. **Figures** (e.g., bar charts, box plots, scatter plots) will illustrate data distributions, group comparisons, and model diagnostics.

Confidence Intervals (95%) will accompany key estimates to indicate precision. **Text** will highlight main findings, including any deviations or unexpected results. These methods will ensure clarity and support interpretation of the study's outcomes.

• Interpretation of Results:

Significant findings (p < 0.05) will be interpreted as evidence of an association or effect, while non-significant findings will not be taken as proof of no effect but rather as inconclusive. Effect sizes and confidence intervals will be emphasized to assess clinical relevance, regardless of statistical significance.

• Potential limitations of the Analysis:

This is a pan European study including patients from 24 sleep centers in 15 countries. New technology will be applied to all patients and health care professionals. The following limitations of the analysis may occur:

- Heterogeneity Across Centers: Differences in referral patterns, clinical routines, experience with remote technology, and treatment traditions across the 24 centers in 15 countries may introduce variability that is not fully accounted for, potentially affecting the comparability of patient populations and treatment effects.
- **Health System Variability**: Diverse healthcare infrastructures and access to care may influence treatment delivery, follow-up, and adherence, impacting outcome measures.
- Cultural and Societal Influences: Variations in cultural attitudes toward symptoms, treatment expectations, and doctor-patient interactions may affect both patient-reported outcomes and clinician assessments.
- **Baseline Differences**: Systematic differences in symptom burden and patient expectations at baseline between countries or centers may confound treatment effects, even after statistical adjustment.
- Physician Perceptions: Differences in physician experience and perception of treatment benefits may influence clinical decision-making and subjective outcome reporting.
- **Generalizability**: The findings may not be generalizable to settings outside of Europe or to centers with significantly different healthcare models or patient populations not studied in the current setting.

14. Changes to the Analysis Plan

• Amendment Procedure:

Any changes to this Statistical Analysis Plan will be documented and reported as follows:

1. Documentation: All changes will be recorded in a version-controlled document, specifying the nature of the change, the rationale, and the date of the change. Each change will be approved by the principal investigator and the study statistician.

2. Reporting: A summary of all changes will be included in the final study report. Major changes will be described in detail, including their potential impact on the study results and conclusions. Any deviations from the original SAP will be transparently reported in publications and presentations of the study findings.

3. Version Control: The SAP document will include a version history table, listing all amendments with corresponding dates and descriptions. This table will be updated with each new version of the SAP.

15. Appendices

• Appendix A: Staff time protocol

WP8 – study

Standard Operation Procedure (SOP) for Staff Time Assessment (Primary Study Variable)

This SOP for the staff time assessment includes the description on how staff time should be assessed in the Sleep Revolution WP8 clinical trial. Importantly, staff time assessment is linked to the diagnostic procedure from start to end of a particular diagnostic activity and the procedure for providing information to the patient at the end of the diagnostic process (diagnosis and treatment recommendation). Notably, time associated with information around the use or follow up of CPAP therapy as the second part of the WP8 study should not be considered in this context.

Primary study endpoint in the WP8 protocol:

"Staff time consumption for the diagnostic procedure comparing the SR assessment and the standard care diagnostic pathways – non inferiority assumption".

Estimates for the power calculation by study protocol:

The different components of the staff time to be captured are summarized in the table below (copied from the study protocol). The table was used for the power calculation of the study.

Table 3: Estimates of staff time (minutes) for the three different diagnostic principles used in the study:PSG=polysomnography, HSAT=Home Sleep Apnea Testing (Cardiorespiratory polygraphy, SleepRevolution=Self Applied Somnography 3 nights)

Work modules	Standard PSG (minutes)	Standard HSAT (minutes)	Sleep Revolution (minutes)
Preparation technical pre/post	15	10	35
Instructions/Hook up	20-40	5-20	5-30
Performance of the sleep test	120-480	0 (patient)	0 (patient)
Evaluation of the sleep test	30-120	5-30	30-90
Questionnaires	5	5	10
Additional equipment	0	0	15
Doctor: interpretation, communication	30-60	15-30	45-60
Staff time: Estimated range of the mean	220-720	40-95	140-240
Staff time: Estimated standard deviation of the mean	180	30	60

1. Activities not monitored in the staff time sheet:

Procedures strictly linked to the clincal study protocol procedure itself but not to the clincal management of the patient

- Patient recruitment: Systematic review of the clinic referrals for potential candidates for study participation
- Patient recruitment: Introduction of the patient to the study objectives, methodologies, patient 's time to respond to questions relation to the general overview of the study procedures, time used to provide information to the patient about details about participation in the study
- Time related to the signed informed consent procedure per se
- The randomisation procedure in general

2. Sleep Revolution diagnostic arm of the study

The following working steps need to be monitored in the WP8 Study Time Sheet

a. BEFORE ARRIVAL OF THE PARTICIPANT

- Assure that information needed to complete the phone call used to recruit the participant has been recorded (some extra but useful pieces of information include: mail, type and brand of the smartwatch in order to determine if the device uses Android or IOS).
- Prepare the box with everything needed for the participant (including instructions, identification number, email and password for the participant's login to the app and site) on the day prior to the study.
- You can set the device (A1S) for auto start

- You may prepare the batteries but it is not recommended to put them in the device or in the pulse oximeter in order to prevent them from loosing power. Förstår inte denna mening. Är det korrekt så som nu justerat.
- CHECK AND CHARGE the Withings Scanwatch. Prepare it according to the guidelines and perform a factory reset before starting it.ember to include the charger in the bag caried by the participant.

b. DAY OF THE STUDY

- Welcome the participant
- Create and start the participant's eCRF on RedCap so you have a checklist and a possibility to note necessary information (unless you want to do the collection manually) (https://wiki.sleep.ru.is/doku.php?id=esada_instructions:timeline_esada_ecrf, https://wiki.sleep.ru.is/doku.php?id=esada_instructions:redcap_instructions#add_edit_a_record _- for_ecrf_project)
- Configure the device (A1S)
- Complete the clinical measurements (height, weight, blood pressure).
- Briefly demonstrate the device to the participant and show where instructions may be found (both the laminated sheet and the QR code for the video instructions)
- Show the login credentials (as previously pointed out it is suggested that the username and password for the participant is printed before handing the device over)
- Assist with the set-up of the Scanwatch
- Assist with downloading and configuring the App
- If needed, show how to access the website
- Send questionnaires via RedCap (The maximum number of reminders to be send to the participant needs to be determined)
- Assure that the participant understands that there are two separate questionnaires, one on RedCap and one on the SleepRevolution web platform
- Inform the patient and arrange for the return of the device

c. AFTER THE DAY OF THE STUDY

- Monitor responses on the RedCap platform
- Monitor responses on the platform (ESQ)
- Download and upload the sleep studies

3. Clinical routine diagnostic arm at the study site

- Please follow the routines of the diagnostic procedures practiced at your clinic (e.g. in-lab PSG or polygraphy)
- . Please use the sleep diagnostic test usually applied for your local diagnostic pathway.
- Prepare the diagnostic test
- Perform diagnostic test
- Analysis of the diagnostic test

4. Meeting between sleep doctor and patient

- Review of questionnaires and sleep diagnostic report by the doctor
- Physical examination.
- Meeting of doctor and patient, clinical interview, information related to diagnosis and treatment
- Medical files: Hospital IT system as a medical note

STUDY TIME PROTOCOL (PRIMARY STUDY OUTCOME VARIABLE)

Study Site:

Patient Study ID:

Patient Initials:

Randomized to (mark correct field) Sleep Revolution first:

Standard care first:

Date of study start:

Procedure	Time (5 minutes intervals only	Initials	
	like 5, 10, 15 etc)		
SLEEP REVOLUTION	PROCEDURE Date of start:		
Preparation of the sleep study and digital			
methodology, initiation of the App and the			
platform			
Patient instruction and handing over of A1S			
to the patient			
I rouble shooting and monitoring of the			
patient during nome sleep studies			
Patient contact at return of equipment			
Upload of data and transfer to data to the			
medical records			
Final scoring of the sleep recordings			
Bring all data together for the patient-doctor			
consultation			
Additional activities not listed above			
Sum of activities in the SR pathway			
······································			
STANDARD CARE	PROCEDURE Date of start:		
Preparation of the sleep study			
Ambulatory sleep study (if applicable): All			
procedures from welcome at the first day			
prior the sleep test and to the discharge after			
successful sleep test procedure (see also			
explanation text)			
In-house sleep study (if applicable):			
All procedures from welcome in the evening			
and discharge in the morning			
Upload of data and transfer to data to the			
medical records (see also explanation text)			
Scoring of the sleep recordings			
Assemble all data for the patient			
consultation with sleep doctor			
Additional activities not listed above			
Sum of activities in the routine pathway			
Communication between sleep doctor and patient			

Patient consultation with the sleep-doctor	
including final diagnosis and treatment	
decision if applicable, documentation in the	
medical record	
Any activity not listed above	
Sum of all activities in the study	

